9.2.2. Study population (Amended 15 July 2022)

The study population will be comprised of all US Medicare beneficiaries who received the RZV vaccine (i.e., exposed) in 2018 through 2020 as well as a random sample of Medicare beneficiaries who did not receive the RZV vaccine but who had at least one preventive care visit (*i.e., comparator group*), as defined in Section 9.7.5. The study population is a longitudinal cohort that is followed over time until they are no longer in Medicare. This means there will be continuity of their data over time, i.e., there is not a new random sample selected each study year.

Study inclusion / exclusion criteria

US Medicare beneficiaries who meet the following criteria will be included in the study:

- 1. Age 65 and older at the date of the RZV vaccination or preventive care visit for the RZV unvaccinated comparator, **AND**
- 2. Enrolled in Medicare due to age or ESRD as the original and current qualifying reason, **AND**
- 3. Continuously enrolled in Medicare Parts A, B, and D fee-for-service for at least 365 days preceding the date of RZV vaccination or preventive care visit for the RZV unvaccinated comparator. Continuous *enrollment* is determined by Medicare enrollment in the month of the RZV vaccination or preventative care visit and *enrollment* in at least 11 of the 12 preceding months.

Beneficiaries enrolled due to ESRD or receiving dialysis are included in the study population as this condition is prevalent among US Medicare beneficiaries aged 65 and older, and this is a subgroup in which RZV use may be common. The requirement for continuous enrollment in Medicare Parts A, B, and D in the 365 days, *allowing one calendar month gap*, before the RZV vaccination or preventive care visit will ensure complete data on all services covered by Medicare on a fee-for-service basis in the baseline study period for the cohort design. Parts A and B provide information on the HOI and Part D provides information on RZV exposure.

Beneficiaries who satisfy the following criteria will be excluded:

- 1. Continuously enrolled only in Medicare Part C in the baseline period, OR
- 2. Enrolled in Medicare due to disability as the original qualifying reason for enrollment.

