9.3. Variables

9.3.1. Exposure measure

RZV exposure will be defined as receipt of at least one dose of RZV for the primary analyses; per-dose analyses will be performed in secondary analyses. RZV vaccination will be identified by means of the national drug code (NDC) and by the Current Procedural Terminology (CPT) code. Part D generally pays for commercially available vaccines. The NDCs from the prescription drug events (PDE) file that will be used to identify RZV exposure as a prescription dispensing in an outpatient pharmacy setting are: 58 160-0828-01; 58 160-0829-01; 58 160 082 311; 58 160-0828-03; 58 160-0829-03; 58 160 082 311; and 58 160-0823-11. The CPT code 90750 for RZV will identify vaccine administration in a Part B (physician office setting) claim. It is anticipated that most will be identified from the PDE file and should only occur in one of the claims files since Medicare will not pay for the same vaccine administration twice, i.e., exposure will not be counted twice.

RZV vaccination records occurring within 27 days after a previous RZV vaccination record (i.e., on days 1-27, where the day of the previous RZV record is day 0) will be considered a duplicate record and will be deleted. The *participant* will be retained for the analytic cohort. For *participants* who receive more than two doses of RZV, even after removal of possible duplicates, we will exclude from analysis RZV doses beyond two per study *participant*.

Preventive care visits for comparison with RZV vaccinations will be identified by means of CPT, ICD-10, and Healthcare Common Procedure Coding System (HCPCS) codes, as shown in Table 2. The presence of any of the below codes qualifies as an eligible "preventive care visit."

Table 2Preventive care visit description for the comparators in the cohort analyses

ICD10	HCPS	CPT	Code Description
			Routine Adult Annual Exam
		99386	Initial comprehensive preventive medicine evaluation and management of an individual including an age and gender appropriate history, examination, counseling/anticipatory guidance/risk factor reduction interventions, and the ordering of laboratory/diagnostic procedures, new patient; 40-64 years
		99387	Initial comprehensive preventive medicine evaluation and management of an individual including an age and gender appropriate history, examination, counseling/anticipatory guidance/risk factor reduction interventions, and the ordering of laboratory/diagnostic procedures, new patient; 65 years and older

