9.3.4. Potential confounding variables and effect modifiers

A confounder is defined as any variable that is associated with both the exposure and the study HOI. Since a confounder cannot be on the causal pathway from exposure to the outcome, all confounders will be captured in the 365 days preceding the index date, i.e., RZV Dose 1 and Dose 2 vaccination date and the RZV unvaccinated comparator preventive care visit for the cohort design. All confounders identified using Medicare enrollment and medical or prescription claims data will be used for covariate adjustment in multivariable models. Propensity score methods will be considered for confounding adjustment, depending on identified imbalances in the observed covariates between the exposed and comparator groups. Confounding variables defined by health care services and comorbidities will be identified using a combination of ICD-10, CPT and HCPCS codes.

- **Demographic variables** will include age, sex, and race and ethnicity (i.e., white, black, Asian, Hispanic, North American Native, and other/unknown based on the US government categories)
- **Healthcare service variables** will include admissions to skilled nursing facilities (SNFs), number of hospitalizations, number of ED visits and Durable Medical Equipment (DME) use. These will be considered to control for potential imbalances between RZV vaccinees and RZV unvaccinated comparators in health impairment requiring more intensive services. The place of service and revenue code on the claim are used to designate the type of service setting.
- **Preventive care services** will include receipt of age-recommended vaccine (e.g., influenza, pneumococcal, and tetanus, diphtheria, pertussis). These will be

considered to control for potential healthy adherer bias that could result in imbalances in healthcare services and prior health seeking behavior patterns between RZV vaccinees and RZV unvaccinated comparators. Table 2 lists the preventive care services. Since mammography, bone mineral density, and colorectal screening are criteria for the unvaccinated comparator selection, these are not included as confounders in the analysis.

- **Medical comorbidities specific to PMR/GCA**. Potential risk factors specific to these conditions may include:
 - Age, which is found to be the strongest risk factor;¹⁹
 - Female sex is found to be a risk factor;¹⁹
 - Race/ethnicity as a significantly lower incidence is reported in African, Asian, Latinos;¹⁹

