9.7.5. Analysis population (*Amended 15 July 2022*)

Population for the SCRI design analyses

Only the cases of new-onset gout, GBS and SVT recorded in the RZV exposed cohort during either the risk or the control windows will be included in the respective HOI SCRI analysis.

Population for the cohort design analyses

The study population for the cohort design will comprise all RZV exposed and RZV unvaccinated comparators with a preventive care visit who satisfy the inclusion criteria. With the cohort design, to exclude prevalent cases of the HOI prior to the index date, all *participants* who had the HOI at any point in the 365-day pre-vaccination baseline period will be excluded.

Generating an index date for unexposed comparators. In an attempt to control healthy user bias among individuals who receive the RZV vaccine, the unvaccinated comparators will be selected from individuals who have at least one preventive care visit. The steps described below will be performed separately for Dose 1 and Dose 2.

- 1. Create a pool of eligible comparators with at least one preventive care visit.
 - The pool of eligible comparators are unvaccinated individuals who had at least one preventive care visit, which is defined as having at least one visit for a routine adult annual exam OR at least one preventive screening intervention performed (Table 2).
 - To ensure complete data for the baseline period preceding cohort follow-up, individuals must be continuously enrolled in Medicare Parts A, B, and D for a minimum of 365 days preceding the preventive care visit. *Continuous enrollment is determined by Medicare enrollment in the month of the preventative care visit and enrollment in at least 11 of the 12 preceding months.* Visits that do not satisfy this criterion will be excluded. For individuals with multiple preventive care visits, only visits that do not meet the eligibility criterion will be excluded. For individuals with only one preventive care visit, the entire person will be excluded if the visit does not meet eligibility criterion.
- 2. Randomly select one preventive care visit from eligible comparators. For an individual to be eligible as a comparator, the individual must not have had RZV at any time in available history prior to or on the day of the preventive care visit.
- 3. The preventive care visit is the index date for the unexposed comparator.

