- Shortened control window for both doses: This will yield a single risk estimate but will use a 3-week (days 43-63) control window for both doses. Dose 1 control window cases will be excluded if also in the Dose 2 risk window.
- Allow a 6-week control window for both doses: This will yield a single risk estimate and will use days 43-84 after Dose 1. The Dose 1 control window cases will be excluded if also in the Dose 2 risk window.

Sensitivity analyses for SCRI design

- Separate dose analysis for Dose 1 and Dose 2: This will yield separate risk estimates for Dose 1 and Dose 2. This risk and control windows for each dose will be defined according to the primary analysis.
- Subgroup analysis of dose compliant individuals who receive both doses according to the US schedule, i.e. within 2 to 6 months: The analysis will be similar to the primary combined dose analysis yielding one risk estimate, but in a subset of the vaccines who receive the vaccine as indicated.

Potential seasonality adjusted SCRI analyses for GBS and gout We will assess any seasonal pattern of RZV vaccination graphically, and will adjust for seasonality in secondary SCRI analyses for GBS and gout, as both of these outcomes are known to have a seasonal pattern.

Analysis of the Cohort Design

Additional inclusion requirements for the cohort design analyses for new onset (i.e., incidence) primary HOIs PMR and GCA include:

- 1. RZV vaccine exposed and a preventive care visit comparator;
- 2. A 365-day look-back from the index date (i.e., vaccination or preventive care visit date) to rule out prevalent cases;
- 3. At least 365 days (1 year) of Parts A, B, and D *continuous* enrollment prior to the index date. *Continuous enrollment is determined by Medicare enrollment in the month of the RZV vaccination or preventative care visit and enrollment in at least 11 of the 12 preceding months.*

Primary analysis of separate doses.

The analysis accounts for the variation in the interval between Dose 1 and Dose 2. The risk period after Dose 1 may overlap in part with the risk period after Dose 2 and/or the baseline period before Dose 2. To mitigate time-window bias, there is similar risk period after each dose.

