Methods to Control for Confounding and Bias. A primary source of confounding in this study are healthy user bias, which refers to the fact that individuals who seek preventive care service may also participate in other healthy behaviors, thus are less likely to experience an outcome. In the cohort analyses, our proposed use of a concurrent preventive care visit as the comparison group will mitigate the effects of healthy user bias on the risk estimate as both RZV vaccinated and unvaccinated will be users of preventive care services.

While other measurable confounding variables that differ between the two groups will be adjusted for in multivariable regression models and possible by using propensity score methods, the risk estimates could still be biased by confounders that were not measured (unmeasured confounders) or not properly measured (residual confounding). A bias analysis is planned to identify how strong an unmeasured confounder must be to explain away the observed effect estimate.

The Dose 2 analysis is conditioned on the subset of individuals who self-select to receive 2 doses within the study period. This may introduce selection bias if there are characteristic differences in measured and unmeasured factors that influence why some individuals receive two doses whereas some only receive one dose. This can underestimate the risk relative to the unvaccinated.

Generalizability. Medicare is the most comprehensive data on older adults, and so the findings will generalize to US adults aged 65 and older. We do not expect appreciable differences between those in the study and those age 65 and older who are not enrolled in Medicare Parts A, B, and D that would affect the HOI risk estimate post-vaccination with RZV.

Sources of random error. The goal is to mitigate bias due to random error. However, it is possible that random sources of error will occur since this is an observational study using secondary claims data. All attempts have been made to ensure appropriate study designs, well-thought out case identification algorithms, appropriate confounder adjustment methods, and planned sensitivity analyses are implemented in the conduct of the study.

Temporal variation. There may be temporal variation due to availability of the vaccine. To address variability in the timing of the vaccine and the preventive care visit, the calendar month-year will be a covariate in the analytic models.

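### Preventive-care use is required of comparators only and is only partly adjusted for, so a difference in health-care contact between the cohort arms is incompletely corrected

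*Combined protocol and SAP*

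**What the plan says.** Section 9.9 names healthy-user bias as a primary source of confounding. It says that the preventive-visit comparator mitigates it, "as both RZV vaccinated and unvaccinated will be users of preventive care services".

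The entry rules are these:

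- Section 9.2.2: "Age 65 and older at the date of the RZV vaccination or preventive care visit for the RZV unvaccinated comparator".
- Section 9.7.5: "the unvaccinated comparators will be selected from individuals who have at least one preventive care visit".
- Section 9.7.6, first cohort requirement: "RZV vaccine exposed and a preventive care visit comparator".
- Section 9.3.1: the drug codes "identify RZV exposure as a prescription dispensing in an outpatient pharmacy setting", and most RZV records are expected from that file.

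On adjustment, section 9.3.4 lists skilled nursing admissions, "number of hospitalizations, number of ED visits and Durable Medical Equipment (DME) use". It continues: "Preventive care services will include receipt of age-recommended vaccine". It then points to Table 2 for the preventive services and states: "Since mammography, bone mineral density, and colorectal screening are criteria for the unvaccinated comparator selection, these are not included as confounders in the analysis". Section 9.7.10 adjusts for variables whose standardized mean difference exceeds 0.10, adds the care setting of the index event, makes propensity scores optional and plans a bias analysis for unmeasured confounding.

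**The concern.** The plan's main device against healthy-user bias acts on one arm. Every comparator begins follow-up at a Table 2 service. A vaccinee may begin it at a pharmacy counter, with no wellness visit or screening on record.

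This matters for PMR and GCA. Each needs two outpatient claims or one inpatient claim plus two glucocorticoid dispensings (Table 3), so being counted as a case depends partly on contact with clinicians. A systematic difference in contact could move the hazard ratio for reasons unrelated to the vaccine. Claims data could measure that difference before the index date in both arms, but the plan does not clearly set out to do so.

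**Working it through.** **Entry rules against the claim.** Sections 9.2.2, 9.7.5 and 9.7.6 all attach the preventive visit to the comparator. A vaccinee must meet the age, enrollment and no-prior-outcome rules and have an RZV claim. No rule requires a Table 2 service of a vaccinee.

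**Reason given for the exclusion.** The three screenings are dropped because they define comparator selection. That applies to the comparator's index event. It does not apply to screening before the index date, which claims show in both arms.

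**Whether other parts of the plan would catch the difference.**

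- The 0.10 rule and the propensity model draw on the 9.3.4 list, which has no outpatient-visit count.
- The descriptive tables in 9.7.4 list vaccines as the only preventive service, and inpatient, ED, DME, hospice, home health and SNF use. An imbalance in office visits or screening would not be shown.
- Care setting is a weak proxy. A pharmacy setting can arise almost only in the RZV arm, so it nearly coincides with exposure.
- The abstract names healthcare visits as a covariate but does not define them, and 9.3.4 does not carry them through as outpatient visits.

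**Reproducing the plan's figures.** The Poisson-regression sample size with exposed share p = 0.2 is

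N = [1.96·√(1/(p(1−p))) + 0.8416·√(1/(1−p) + 1/(p·RR))]² / (rate·T·(ln RR)²).

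For PMR with RR 2, rate 0.000405 and T = 0.5 year:

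- Numerator: (1.96 × 2.5 + 0.8416 × 1.9365)² ≈ 42.64.
- Denominator: 0.0002025 × 0.4805 ≈ 0.0000973.
- N = 438,239 at full precision, as in Table 5.

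All nine rows of Table 5 reproduce to within one person. With T = 1 they come out at half the stated size, so the baseline figures act as rates per person-year.

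**Precision at the projected size** (section 9.2.2: a little over 2 million vaccinees, 8 million comparators):

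- PMR events under the null: 0.000405 × 0.5 × 2,000,000 = 405, and × 8,000,000 = 1,620.
- SE(log HR) = √(1/405 + 1/1,620) = 0.056, and 1.96 × 0.056 = 0.109, so the 95% CI is about ±11%.

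**Illustrative bias.** Let pv be the share of vaccinees in preventive contact and D the ratio of the diagnosis rate with contact to that without. All comparators are in contact. The documents give neither pv nor D, so both are assumptions. With no adjustment, the observed HR equals the true HR times

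factor = (pv·D + 1 − pv)/D = pv + (1 − pv)/D.

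| pv | D | Factor | True PMR HR 2 seen as | True GCA HR 3 seen as |
|---|---|---|---|---|
| 0.9 | 1.1 | 0.99 | 1.98 | 2.97 |
| 0.7 | 1.5 | 0.90 | 1.80 | 2.70 |
| 0.5 | 2.0 | 0.75 | 1.50 | 2.25 |

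At the Table 5 sample sizes, power in these three cases falls from 80% to 79%, 63% and 31% for PMR, and to 79%, 68% and 45% for GCA.

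If contact instead marks lower true risk, D is below 1. The reciprocals of the D values above give 0.9 + 0.1 × 1.1 = 1.01, 0.7 + 0.3 × 1.5 = 1.15 and 0.5 + 0.5 × 2.0 = 1.50. If pv = 1 or D = 1 there is no bias.

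**Could a null effect look protective for PMR?** With pv = 0.75 and D = 1.5 the factor is 0.917, and ln(0.917)/0.056 ≈ −1.6, which is not significant. With pv = 0.6 and D = 2 the factor is 0.80, and ln(0.80)/0.056 ≈ −4.0, which is.

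**The case against.** The plan has a fair answer on several counts.

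- Sections 9.3.4 and 9.7.4 class vaccination as a preventive service, so an RZV recipient is a preventive-care user in that sense. This stands as a reading of the 9.9 sentence. However, a pharmacy dispensing is not equivalent to the clinician or screening contact required of every comparator.
- Vaccines, hospital, ED, SNF and DME use are planned covariates. The vaccines are included expressly against healthy-adherer bias. Residual confounding is acknowledged and a bias analysis is planned. This stands, so the difference is partly corrected. The bias analysis is aimed at unobserved factors, though, and this one is observable.
- The exclusion names three screenings. Routine and wellness exams are neither named as covariates nor ruled out.
- Two glucocorticoid dispensings limit incidental coding, and one inpatient claim can also qualify a case. This may keep D close to 1.
- The target risks would survive. Even at a factor of 0.75, a PMR HR of 2 is seen as 1.50, and ln(1.50)/0.056 ≈ 7.2 at the projected size.

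A reader might infer that the hazard ratio carries an uncorrected bias that hides harm. The documents do not support that. No figure for vaccinees' preventive use is given, some adjustment is planned, and section 9.9 itself says that people who seek preventive care are less likely to have an outcome, which would push the ratio upward.

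**Conclusion.** The point holds as a gap in comparability. The balance that section 9.9 relies on is not secured by any entry rule for vaccinees. Three measurable services are left out of adjustment for a one-sided reason, and outpatient contact is neither a listed covariate nor tabulated by arm.

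The direction is open and the size unknown. Under the assumed ranges (pv 0.5 to 0.9, D 1.1 to 2.0, no adjustment) the factor is 0.75 to 0.99 if contact raises detection, and above 1 if contact marks lower risk. The planned covariates would absorb some of this.

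The practical risk concerns modest effects. A distortion of about 10% is similar to the half-width of the PMR interval, so it could blur a small excess. A misleading significant result appears only towards the extreme end of the assumptions. The sample sizes in Table 5 are sound on their own inputs and are not in question.

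**What to change.** 1. Tabulate by arm, with standardized mean differences, outpatient clinician visits and Table 2 services before the index date. Put the outpatient-visit count in days −365 to −1 into the cohort Cox model.
2. Replace the blanket exclusion in 9.3.4 with adjustment for prior screening. A plain 365-day look-back that omits the index day would undercount comparators whose index event is the annual service, because last year's visit may fall just outside it. Use a longer look-back where enrollment allows and report it as a sensitivity model. Data start in January 2017, so a two-year look-back is possible only for index dates from 2019.
3. Prespecify a sensitivity analysis limiting vaccinees to those with at least one Table 2 service in days −365 to 0, against the existing comparators. It makes both arms preventive-care users. It does not equalise timing, since the comparator's service is always on day 0.
4. Reword 9.9 to say that a preventive visit is required of comparators only.

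The cost is a few claims-based covariates, one more analysis and a smaller vaccinated group in item 3. That group still meets the Table 5 requirement if at least 87,648/2,000,000 = 4.4% (PMR) or 144,673/2,000,000 = 7.2% (GCA) of vaccinees qualify.

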9.10. Other aspects

To comply with regulatory requirements and GSK standards, administrative obligations relating to protocol amendments, protocol administrative changes and termination of the study must be fulfilled.

Record retention

Data files and programs will be retained on PRC secure servers for the duration of the study as stipulated in the DUA. However, a DUA may be renewed for an indefinite duration of time, depending upon the study needs.

During project closeout, project specific programs, output, data sets and documentation are archived unless stipulated otherwise. A custodial server assessment determines what, if any, resources remain after this process.

Upon completion of research activities or expiration of the DUA, data resources covered by the DUA must be destroyed to prevent breach of confidentiality. This data destruction is then certified and reported to CMS within 30 days. Additional project files may be preserved on the PRC server archive for up to 3 years following the closure of the DUA; however, the DUA may remain active for as long as needed for the study purpose and requirement to maintain the data for a specified period of time. In this study, the project files will be preserved for 15 years, per contractual agreement.

Quality assurance

The PHSR department and PRC are guided the management concept of Total Quality Management. PHSR and PRC highly value quality assurance measures utilizing standardized project management procedures managing projects and project files. Best practices have been established to assist in assuring outputs are as accurate as possible.

Posting of information on publicly available clinical trial registers and publication policy.

Observational studies evaluating a product:

- The key design elements of this protocol and results summaries will be posted on the GSK Clinical Study register in compliance with GSK policy according to the timelines described below.
 - Protocol summaries will be registered prior to study start.
 - Results summaries along with redacted protocol and SAP will be posted within 12 months of analysis completion date.
- Where required by regulation, summaries will also be posted on applicable national or regional clinical trial registers.
- Where required by applicable regulatory requirements, an investigator signatory will be identified for the approval of the study report, and provided reasonable access to statistical tables, figures, and relevant reports. GSK Biologicals will also provide the investigator with the full summary of the study results.

CONFIDENTIAL

• GSK also aims to publish the results of these studies in the searchable, peer-reviewed scientific literature; manuscripts are submitted within 18 months of the completion of the analysis. Any publications will follow guidelines, including those for authorship (e.g., guidelines established by the International Committee of Medical Journal Editors 2018) and for reporting of observational studies in epidemiology (e.g. Strengthening the Reporting of Observational Studies in Epidemiology (STROBE,) 2007)³⁹.

PASS studies:

- Protocol summaries for non-interventional post-authorization safety studies will be registered along with redacted protocol in the EU PAS register prior to study start.
- Redacted Clinical Study Report (CSR) will be submitted in the EU PAS register within 12 months of end of data collection.
- Where required by applicable regulatory requirements, an investigator signatory will be identified for the approval of the study report, and provided reasonable access to statistical tables, figures, and relevant reports. GSK Biologicals will also provide the investigator with the full summary of the study results.

Provision of study reports to regulatory authorities

The final study report will provide an overview of the study background, objectives, methods, and findings and will be submitted to regulatory agency authorities by the vaccine manufacturer. Final study results, as well as the main methodological components developed as part of this study, will be disseminated as oral or poster presentations at scientific meetings and as peer-reviewed publications

